4 STATISTICAL ANALYSIS

4.1 Statistical Analysis Methods

Data management, tabulations, graphics, and statistical modeling in carried out with R language (<http://www.r-project.org>). R language is described more detailed in report "R: Regulatory

Compliance and Validation Issues: A Guidance Document for the Use of R in Regulated Clinical Trial Environments" (<http://www.r-project.org/doc/R-FDA.pdf>)

A separate statistical analysis plan (SAP) including detailed statistical analysis and outputs will be produced by EPID research prior to performing any analysis.

Study population: The study population will be described at baseline (start of follow-up) using by previous drug exposure and other covariates.

Study outcomes: All study outcomes will be summarized by drug exposure and other covariates.

Drug exposure: Drug exposure starts at date of purchase. The length of the exposure period is calculated as $DDD/dose \times 1.5$, where DDD (daily defined dose) is the total amount purchased and “dose” is the amount used daily (one for an average person). For the first purchase “dose=1” and for other purchases the “dose” is calculated from previous use by dividing the previous DDD with the time between the present and the previous purchase.

The impact of the multiplier 1.5 in the construction of drug exposure will be evaluated for the primary objectives in sensitivity analyses by using multiplier values 1.25, 1.5 and 2. We will also perform a sensitivity analysis for the primary objectives by including only those patients with at least two purchases of prescriptions within a clinically meaningful timeframe of 3 months after the index date.

INR levels: Daily INR levels are calculated:

- 1) As the previous recorded INR measurement
- 2) By linear interpolation between two consecutive INR measurements. If the gap between the measurements is more than 60 days the previous measurement is applied.

Daily INR estimates are categorized into levels: under 2.0, 2.0-3.0, over 3.0. In addition when appropriate a finer categorization is used: under 1.5, 1.5-2.0, 2.0-3.0, 3.0-4.0, 4.0-5.0, 5.0-9.0, and over 9.0. This finer categorization will be used only in the analysis of the primary objectives.

Time in therapeutic range (TTR): The INR target value for AF patients is 2.0-3.0. In addition for stroke, systemic thromboembolic events, and myocardial infarction INR target above 2.0 is considered and for bleeding events INR target under 3.0 is considered.

TTR will be calculated as

- 1) the percentage of time during which the interpolated INR values lie between 2.0 and 3.0¹³ and this is calculated using INR measurements during the previous 1, 2, 3, 6 and 10 months, and
- 2) the percentage from previous 5 and 10 INR measurements that are between 2.0 and 3.0.

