4.1.2 Secondary Objectives

Objective 1: Stratified incidence rates with 95% CIs will be estimated for stroke, systemic thromboembolic events, myocardial infarction, and bleeding events within the strata of the exposure variables (INR levels and TTR categories) and other covariates during the first 90 days after initiation of warfarin treatment.

The crude and adjusted hazard ratio (HR) estimates with 95% CIs and P-values will be estimated separately within the INR levels and TTR categories using the conventional Cox's proportional hazards model adjusting for other covariates, including history of AF prior the index date. For INR the category 2.0–3.0 will be used as the reference category. Similarly for TTR the category $\geq 60\%$ of time will be used as the reference category.

Objective 2: Stratified incidence rates with 95% CIs will be estimated for stroke, systemic thromboembolic events, myocardial infarction, and bleeding events within the strata of the exposure variables (INR levels and TTR categories), and time from AF diagnosis to time of initiation of warfarin treatment (categories: under 6 months, 6-12 months, over 12 months). For INR the category 2.0–3.0 will be used as the reference category. Similarly for TTR the category $\geq 60\%$ of time will be used as the reference category.

Also, time from AF diagnosis to time of initiation of warfarin treatment will be added as an additional covariate to the Cox's proportional hazards model.

Objective 3: Stratified incidence rates with 95% CIs will be estimated for stroke, systemic thromboembolic events, myocardial infarction, and bleeding events within the strata of other covariates for warfarin patients after stopping warfarin treatment. Warfarin treatment is considered ended if there is more than 2 months gap since last warfarin exposure and INR measurement. Sensitivity analysis with 1 and 3 months gaps will be performed to study the robustness of the definition.

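### The exposure rule takes daily warfarin use from the last refill interval alone, with no bound and no reset after a treatment gap, so a restart purchase after a long gap counts as prolonged exposure

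*Protocol*

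**What the plan says.** Protocol Section 4.1 starts exposure at the purchase date and gives a formula for its duration: "The length of the exposure period is calculated as" DDD/dose × 1.5, where DDD is the total amount purchased. The daily dose is set in two ways. "For the first purchase “dose=1” and for other purchases" it is "calculated from previous use by dividing the previous DDD with the time between the present and the previous purchase". The section gives no minimum or maximum dose and no cap on length. It provides no return to dose=1 after an interruption and does not say whether overlapping periods are merged or replaced.

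For Secondary Objective 3 (Section 4.1.2) the stop rule is: "Warfarin treatment is considered ended if there is more than 2 months gap since last warfarin exposure and INR measurement". I read this as requiring both gaps.

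Three sensitivity analyses bear on the construction:
- Section 4.1: "The impact of the multiplier 1.5 in the construction of drug exposure will be evaluated for the primary objectives", "using multiplier values 1.25, 1.5 and 2".
- Section 4.1: a subset "including only those patients with at least two purchases of prescriptions within a clinically meaningful timeframe of 3 months after the index date".
- Section 4.1.2: "Sensitivity analysis with 1 and 3 months gaps will be performed to study the robustness of the definition".

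Section 3.4.3 adds that hospital and institutional stays will be considered when discontinuation is defined. It does not mention them for the dose calculation.

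**The concern.** The rule cannot tell a patient who takes little warfarin from one who took none for part of the interval. A long interval lowers the estimated daily use, and the next pack is then assumed to last correspondingly longer. The longer someone was off treatment, the longer the restart purchase counts as exposure.

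This conflicts with the protocol's own stop rule: the same interval can be ended treatment under Section 4.1.2 and previous use under Section 4.1.

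The stake is Secondary Objective 3, the risk after stopping warfarin. If a patient restarts, stops again and then has an event, both the event and the person-time before it fall on the treated side. Time since discontinuation (Section 3.4.2) and concomitant use of interacting drugs (Section 3.4.3, which refers to the exposure definition in Section 4.1) use the same periods.

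**Working it through.** **Inputs.** From Section 4.1: the length formula, dose=1 for the first purchase, and the multipliers m = 1.25, 1.5 and 2. From Section 4.1.2: the 2-month gap, taken as 61 days. Assumption, not in the documents: 100 DDD per pack. The protocol states no figure of its own on this point to reproduce.

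**Algebra.** For purchase k after an interval g:
- dose = DDD(k−1) / g
- length = m × DDD(k) / dose = m × g × DDD(k) / DDD(k−1)

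With equal packs the pack size cancels and length = m × g.

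| Preceding interval (days) | Implied dose | m = 1.25 | m = 1.5 | m = 2 |
|---|---|---|---|---|
| 100 | 1.00 | 125 | 150 | 200 |
| 180 | 0.56 | 225 | 270 | 360 |
| 365 | 0.27 | 456 | 548 | 730 |
| 400 | 0.25 | 500 | 600 | 800 |
| 730 | 0.14 | 913 | 1095 | 1460 |

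At m = 1.5 the length passes one year at an interval of about 244 days (365/1.5 = 243.3) and two years at about 487 days (730/1.5 = 486.7). Unequal packs can make it longer: 30 DDD followed by 100 DDD after 180 days gives 1.5 × 180 × 100/30 = 900 days.

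**The two sections applied to one patient.** First purchase on day 0, restart on day 400, no INR test between the end of the first exposure and the restart.
- First exposure: 100/1 × 1.5 = 150 days. Treatment counts as ended from about day 150 + 61 = 211.
- Days 211 to 400, about 189 days, are therefore off treatment under Section 4.1.2.
- At the restart, Section 4.1 spreads the first 100 DDD over all 400 days: dose = 0.25, length = 100/0.25 × 1.5 = 600 days.
- If the patient buys no more, the second stop is recognised 600 + 61 = 661 days after the restart, about 22 months.
- With dose=1 at the restart: 150 + 61 = 211 days, about 7 months. The difference is 450 days.

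**Do the sensitivity analyses reveal this?**
- Multipliers: 500/125 = 600/150 = 800/200 = 4. The fourfold inflation relative to dose=1 is the same at every value, and these analyses are stated for the primary objectives only.
- Stop gaps of 1 and 3 months (about 30 and 91 days) move the second stop to 630 and 691 days. They begin only after the 600 days have run.
- The two-purchase subset concerns the first 3 months after index and does not limit later intervals.

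**A further purchase.** If the patient buys 100 DDD again 100 days after the restart, dose returns to 1 and the new period ends at 100 + 150 = 250 days. Whether it replaces the 600-day period or is merged with it is not stated. If merged, the 600 days remain.

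**The case against.** The best case against the point is that it describes a narrow pattern: a long gap, a restart purchase, then a second stop. The first stop is dated without this error. Detailed analysis is deferred to a SAP, and hospital stays are to be considered for discontinuation. The documents give no frequency of such gaps, so no bias in Objective 3 can be quantified. The narrowness and the unknown frequency stand, and they limit the size of the claim. The SAP argument does not remove it, because the protocol itself fixes the formula. The hospital provision does not reach the dose calculation.

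A reader might infer three stronger points that the documents do not support.

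- **That an event's own INR test reclassifies that event as on-treatment.** An event within the 2-month gap is on-treatment in any case. For an event on day 100, with exposure and last INR both ending on day 0, the stop condition was met at about day 61, before the admission test existed. Section 3.4.1 ends follow-up for each outcome at its event. What remains is an effect on a different, later outcome: a bleed with an INR test on day 40 would move the recognised stop for stroke from about day 61 to day 101 (40 + 61).
- **That regular users with an early refill appear as stopped.** Equal packs bought 5 days apart do give the second one only 1.5 × 5 = 7.5 days. But the stop rule also needs an INR gap, and if periods are merged the first purchase still covers its 150 days.
- **That the primary results are biased.** Primary follow-up runs to 31-Dec-2011 regardless of exposure and the comparison is by INR and TTR. The multiplier sensitivity for the primary objectives suggests some role for exposure, but an effect is not shown.

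**Conclusion.** The point holds for patients who restart after a gap. The stated rule makes the next exposure 1.5 times the preceding interval (equal packs), so a 400-day gap yields 600 days and a second stop recognised about 22 months after the restart purchase. This rests on the equal-pack assumption, on no later purchase changing the period, and on reading the stop rule as requiring both gaps.

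Off-treatment time and events are then counted as on-treatment in Secondary Objective 3, time since discontinuation and concomitant-use periods. None of the planned sensitivity analyses would expose it. The overall effect on Objective 3 cannot be sized from the documents. It should be corrected before analysis.

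**What to change.** - Do not use an interval classed as ended treatment, or hospital time within it, to estimate daily use.
- After such a gap, either return to the first-purchase value dose=1 (in the example 150 days, or 125 to 200 over the multipliers, whatever the gap) or estimate use over several earlier on-treatment intervals with a stated lower and upper bound.
- Pool purchases made on the same day, where the interval is zero and the formula undefined, or nearly so. A 14-day pooling window, a 12-month look-back or 5th and 95th percentile bounds are only examples. The values should be set before analysis.
- State whether overlapping periods are merged or replaced.
- Extend the multiplier sensitivity analysis to Secondary Objective 3.
- As a minor addition for Objective 3, decide treatment end using only INR tests taken before an outcome admission, so that an admission for one outcome does not delay the recognised stop for another.

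The cost is programming and a paragraph of protocol or SAP text. No new data are needed.

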3.3 Data Source/Data Collection Process

The study timelines are presented in the picture below:

Figure 3.3-1: Study Timelines

[figure not shown]

Table 3.3-1: Study Registers

Register	Register Holder	Information obtained
National Prescription Register	Kela – The Social Insurance Institution of Finland	Drug purchases (ATC codes)
National Reimbursement Register	Kela	Reimbursement decisions 207 for chronic arrhythmias (for population characterization)
Finnish Care Register, HILMO	National Institute for Health and Welfare	Diagnoses (ICD10 codes) and date of diagnosis
National Causes of Death Register	Statistics Finland	Time of death and causes of death (ICD-10 codes)
Laboratory databases	HUSLAB + other hospital laboratories	INR measurements and other relevant laboratory values
Finnish Cancer Registry	National Institute for Health and Welfare	Cancer diagnosis (ICD-O-3 codes) and date of diagnosis
Population Register	Population Register Center	Places of domicile 12 months prior to and on index dates.
Social HILMO	National Institute for Health and Welfare	Information (dates) about institutionalization (other than hospitalization)

- Data will be requested from the registry holders ([Table 3.3-1](#)) based on the study protocol.
- Data permits will be requested from each registry holder based on the study protocol and ethical approval.
- Approval of Ethical Review Board of Hospital District of Helsinki and Uusimaa (HUS) will be requested to cover the nationwide study.
- This is a fully register-based study and patients will not be contacted in any phase of the study.
- Warfarin exposure will be defined by Kela, who then will convert the patient IDs to study IDs (SIDs). Kela will then send the IDs and the SIDs to other register holders: Statistics Finland, National Institute for Health and Welfare, Statistics Finland, Population Register Center, and central hospital laboratories included in the study.
- EPID Research will receive unidentifiable data including SIDs only. All patient data handled by the researchers are then anonymous which ensures full data protection of the patients.

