3.4 Definitions of Study Variables

3.4.1 Outcomes/Endpoint Variables

The studied primary outcomes/endpoint variables of interest are defined through ICD-10 diagnosis codes (hospitalizations and deaths) or ICD-O-3 codes (cancers). See [Appendix 1](#) and [2](#) for more detail.

The time to event for each primary outcome will be calculated as the time from the index date to the time of the diagnosis of the outcome when such an event occurs during the follow-up.

Index date is defined as the date of first purchase of warfarin after 01-Jan-2007. Follow-up of the patients starts on the index date, and ends on 31-Dec-2011, at time of death or at time of emigration whichever occurs first. Treatment and comorbidity history is gathered from the period 01-Jan-2005 to 31-Dec-2006.

Primary outcomes:

- Stroke
- Other systemic thromboembolic events excluding stroke
- Myocardial infarction
- Bleeding events
- Mortality all-cause
- Mortality (stroke)
- Mortality (myocardial infarction)
- Mortality (systemic thromboembolic events excluding stroke)
- Mortality (bleeding events)

The studied secondary outcomes/endpoint variables of interest are anemia and renal impairment.

Time to anemia is defined as the time from index date to time of first decrement of 20 g/L in haemoglobin or time when haemoglobin is under the reference value.

Time to renal impairment is defined as the time from index date to time when creatinine is under the reference value.

Secondary outcomes

- Anemia
- Renal impairment

In the statistical analysis follow-up for each time to event outcome continues until the time of the event, death, emigration or 31-Dec-2011 whichever comes first.

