4.1.1 Primary Objective

Objectives 1-3: Stratified incidence rates with 95% confidence intervals (CIs) will be estimated for each primary endpoint within the strata of the exposure variables (INR levels and TTR categories) and other covariates, including history of AF prior the index date.

The crude and adjusted hazard ratio (HR) estimates with 95% CIs and P-values will be estimated separately within the INR levels and TTR categories using the conventional Cox's proportional hazards model adjusting for other covariates. For INR the category 2.0–3.0 will be used as the reference category. Similarly for TTR the category $\geq 60\%$ of time will be used as the reference category.

The objectives will be evaluated separately for the prevalent warfarin user population and the new warfarin user population. The new warfarin user population consists of those patients who initiate warfarin treatment during the follow-up (01-Jan-2007 to 31-Dec-2009).

A further sensitivity analysis will be performed where the adjusted HRs are estimated stratifying by the history of AF prior to the index date.

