5 STUDY LIMITATIONS/STRENGTHS

Finland has a well-developed population register system with tens of years of longitudinal follow-up data. The persons are identified in the registers with a unique personal identification number enabling linkage between different registers. These data has not been collected for study purposes, which may affect the quality of the data. However, these registers have been considered reliable for scientific research purposes.

Only those citizens that have been living in Finland for 12 months prior to index date will be included in the study.

No exact prescribed dosing information is available. Dosing is assumed based on the information of purchases and package sizes with defined daily doses (DDDs).

Coverage of the Prescription Register containing reimbursement information of all permanent residents of Finland is about 97%. Missing data includes relatively inexpensive packages which are not reimbursed. Fully reliable information on eg, acetylsalicylic acid use is then not available.

Medications used during hospitalizations are not available. However, based on the hospital care register the hospitalization periods can be taken into account to define gaps in the drug treatment periods.

No nationwide database about laboratory measurements is available. The laboratory data is then collected from separate local central laboratories. All laboratory values for particular patients may then not be available. Also changes in places of domicile may affect the follow-up of the patients. On the other hand, previous published surveys on the subject have not included INR follow-up to this extend.

To avoid selection bias, the cohort time (years 2007 to 2009) was chosen to avoid complication of patients switching from warfarin to newer anticoagulant medications eg, dabigatran.

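### As written, the primary INR-level analysis does not exclude time after warfarin has stopped, and part of that time can fall in the INR 2.0-3.0 reference group

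*Protocol*

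**What the plan says.** Protocol section 4.1 gives two ways to assign a daily INR. Method 1 is "As the previous recorded INR measurement". Method 2 is linear interpolation between consecutive measurements, with the exception "If the gap between the measurements is more than 60 days the previous measurement is applied". Neither states a maximum age for a carried value.

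Section 3.4.1 fixes the end of person-time: "In the statistical analysis follow-up for each time to event outcome continues until the time of the event, death, emigration or 31-Dec-2011 whichever comes first". The synopsis and section 3.1 give the same end of follow-up, apart from the event itself. Stopping warfarin is not in any of these lists.

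Section 4.1.1 estimates rates "within the strata of the exposure variables (INR levels and TTR categories) and other covariates", with INR 2.0-3.0 as the reference for hazard ratios. No off-warfarin state is named.

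A stopping rule does exist, in section 4.1.2 under Secondary Objective 3: "Warfarin treatment is considered ended if there is more than 2 months gap since last warfarin exposure and INR measurement". Gaps of 1 and 3 months are sensitivity analyses there. The rule is not invoked for the primary objectives.

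Section 4.1 also builds purchase-based exposure periods with a multiplier of 1.5 and varies it (1.25, 1.5, 2) for the primary objectives. Section 3.4.2 lists time since discontinuation as a variable.

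**The concern.** The primary question is risk by INR level on warfarin. An INR recorded before stopping says nothing about anticoagulation months or years later. If such days stay in the INR strata, off-treatment stroke, bleeding and death rates are mixed into all three categories, including the denominator of every hazard ratio.

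The time involved can be long. Index dates run from 2007 to 2009 and follow-up to the end of 2011, so each patient has 2 to 5 years of potential follow-up. Under method 1, a patient who stops in 2008 with a last INR of 2.5 remains in the reference group until the end of 2011. The same days would be analysed as time after stopping in Secondary Objective 3, so two analyses in one report would give them contradictory labels.

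**Working it through.** **1. The protocol's own figures.** Section 4.2: 3 million × 1.6% × 67% = 32 160, given as 32 000; × 3 years = 96 000 person-years. The INR shares 21.7/63.6/14.7% give 20 832, 61 056 and 14 112, rounded in the protocol to 21 000, 61 000 and 14 000. These sum to 96 000, so the sample-size section allots all follow-up to an INR category and sets none aside as off-warfarin.

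Table 4.2-1 gives 78.6% power for relative risk 1.20 at 1.5 events per 100 patient-years (32 000 patients). Power = Φ(|ln RR|·√(D·p(1−p)) − 1.96), with D = 82 000 × 0.015/0.985 = 1 249, p = 21/82 and two-sided alpha 0.05 (assumed, not stated), gives Φ(2.81 − 1.96) = 80.3%. All 36 table cells are matched within 2 points.

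**2. Inputs for the illustration.** From the protocol: INR shares 0.217 and 0.636, reference rate 1.5, relative risk 1.20 (low-INR rate 1.8). Assumed, because the documents do not give them: *off* = share of follow-up off warfarin; *m* = off-warfarin stroke rate divided by the reference rate; *a*, *b* = share of stoppers whose last INR was below 2.0 or 2.0-3.0.

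**3. Formulae** (*on* = 1 − *off*).
- Reference rate = (on·0.636·1.5 + off·b·1.5·m) / (on·0.636 + off·b)
- Low-INR rate = (on·0.217·1.8 + off·a·1.5·m) / (on·0.217 + off·a)

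Example, off = 0.10, m = 3, a = b = 0.45: reference 1.0611/0.6174 = 1.72; low 0.55404/0.2403 = 2.31; ratio 1.34.

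**4. Results with 10% off-warfarin time, true ratio 1.20.**

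| Last INR <2.0 / 2.0-3.0 | m | Reference rate | Low-INR rate | Observed ratio |
|---|---|---|---|---|
| 21.7% / 63.6% | 1.5 | 1.58 | 1.85 | 1.17 |
| 21.7% / 63.6% | 2 | 1.65 | 1.92 | 1.16 |
| 21.7% / 63.6% | 3 | 1.80 | 2.07 | 1.15 |
| 35% / 55% | 2 | 1.63 | 1.98 | 1.22 |
| 35% / 55% | 3 | 1.76 | 2.21 | 1.25 |
| 45% / 45% | 2 | 1.61 | 2.02 | 1.26 |
| 45% / 45% | 3 | 1.72 | 2.31 | 1.34 |

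With m = 1.5 the last two splits give 1.19 and 1.21, almost no bias. With 20% off-warfarin time, the first split gives 1.15 to 1.11 (m = 1.5 to 3) and the other two 1.21 to 1.40 (m = 2 to 3). The reference rate is inflated in every case; the ratio moves either way.

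**5. Power, first split, 10% off-warfarin time.** By Schoenfeld's formula with events at the resulting rates, power is 81.4% with no off-warfarin time, 71.5% to 66.3% with it kept in the strata, and 77.2% with it removed (ratio 1.20, fewer events).

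**6. TTR.** Section 4.1 defines TTR over the previous 1 to 10 months, or over the previous 5 and 10 measurements. The windowed version has no input once the last INR is older than the window, so it cannot persist for years. The count-based version can.

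**The case against.** The strongest reply is that exposure was meant to bound the primary analysis. Varying the 1.5 multiplier for the primary objectives would do little or nothing to the INR results if unexposed days stayed in the strata. Time since discontinuation is a listed variable, hospital and institution dates feed the definition of discontinuation, and a separate statistical analysis plan is announced. This stands as evidence of intent. However, no section restricts primary person-time to exposed days, and section 3.4.1 states an explicit analysis rule that does not. The sections must be reconciled.

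A reader might infer more than the text supports in four ways:
- That the 60-day sentence carries values to the end of 2011. It addresses gaps between two measurements; only method 1 carries the last value on without limit.
- That off-warfarin time lies mostly in the reference group. The 63.6% is a share of all INR measurements, not of last values before stopping.
- That the hazard ratio is inflated. The table shows attenuation under the protocol's own INR split.
- That every TTR analysis is affected for years. Only the count-based version is open to this.

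Section 5 says the 2007-2009 window "was chosen to avoid complication of patients switching from warfarin to newer anticoagulant medications". This limits cohort entry, while follow-up continues to the end of 2011. The amount of switching in that period cannot be judged from the documents.

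**Conclusion.** The point holds as a defect of the written rules: follow-up ignores discontinuation, method 1 has no age limit, method 2 is silent after the last INR, and the primary analysis has no off-warfarin state. Whether the analysts would have restricted to exposure periods anyway is unknown.

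The size is conditional. For 10% off-warfarin time and a true ratio of 1.20, the observed ratio is about 1.15-1.17 if last INRs follow the 21.7/63.6/14.7 split (off-warfarin rate 1.5-3 times the reference), or 1.22-1.34 if 35-45% of stoppers had a last INR below 2.0 (2-3 times). Many of these shifts are large against the 10-20% differences the study is powered to detect. The off-warfarin share, rate and last-INR split are all assumptions, so neither direction nor magnitude can be claimed from the documents.

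**What to change.** - In the primary INR and TTR analyses, end person-time at the treatment-end definition already in section 4.1.2 (2-month gap, with 1 and 3 months as sensitivity), or move later time to a separate off-warfarin state. State how this relates to the exposure periods and their multiplier.
- Set a maximum age for a carried-forward INR under both methods, and class later days as INR unknown, outside the reference. The 60 days already used for interpolation is one candidate; the value is a convention to be fixed in advance.
- Apply the same limit to the TTR based on the previous 5 and 10 measurements.
- Keep the uncensored analysis as a sensitivity analysis.

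The cost is mainly wording, with some loss of person-time and events. Censoring at stopping may be informative, since patients may stop because of bleeding or decline; this favours the separate off-warfarin state.

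Optional, and needing additional register data: emigration dates (a stated censoring event not listed in Table 3.3-1), domicile after index (the table lists only "Places of domicile 12 months prior to and on index dates"), and purchases of newer anticoagulants, whose codes are in neither section 3.4.2 nor Appendix 3.

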3 STUDY DESIGN

3.1 Overview of Study Design

The study with cohort design is conducted as a nationwide retrospective register-based linkage study using data obtained from the Finnish health care registers. The study population consists of all AF patients using warfarin with INR measurements in selected hospital district areas in Finland between 01-Jan-2007 and 3-Dec-2009.

Index date: Index date is defined as the date of first purchase of warfarin after 01-Jan-2007.

Follow-up period: Follow-up of the patients starts on the index date, and ends on 31-Dec-2011, at time of death or at time of emigration whichever occurs first.

History period: Treatment and comorbidity history is gathered from the period 01-Jan-2005 through 31-Dec-2006.

The key milestones of the study process are given below (Table 3.1-1). Note that the timelines are estimates only and are subject to change depending on the duration of the data permission processes and actual receipt of the data from the register holders.

Table 3.1-1: Study Timelines

Milestone	Anticipated date
Study protocol approved	4-Mar-2013
Registration in the ENCePP e-Register	30-Apr-2013
Ethics committee approval	30-Apr-2013
Data permit approvals	30-Jun-2013
Receipt of data from register holders	30-Sep-2013
Final study report	30-Dec-2013

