3.2.1 Inclusion Criteria

Patients fulfilling the following criteria are included in the study:

- Patient has purchased warfarin (Anatomical Therapeutic Chemical classification (ATC) code B01AA03) between 01-Jan-2007 and 31-Dec-2009,
- Patient has at least one INR measurement available between 01-Jan-2007 and 31-Dec-2009, and
- Patient has a International Classification of Diseases (ICD-10 version 10) diagnosis code I48 for AF between 01-Jan-2005 and 31-Dec-2009.

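### The daily INR level has no maximum age: an old INR is carried forward indefinitely and no day is ever classed as unknown, which misclassifies the exposure of all three primary objectives

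*Protocol*

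**What the plan says.** Protocol section 4.1, under INR levels, defines the daily INR in two ways.

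- Method 1: "As the previous recorded INR measurement", with no time limit.
- Method 2: linear interpolation between consecutive tests, with one exception: "If the gap between the measurements is more than 60 days the previous measurement is applied".

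Every estimate is then placed in a level: "Daily INR estimates are categorized into levels: under 2.0, 2.0-3.0, over 3.0". A finer split is added for the primary objectives. Neither set has a level for a stale or missing value.

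Three other provisions determine how far a value can be carried:

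- Section 3.2.1 requires a single test for entry: "Patient has at least one INR measurement available between 01-Jan-2007 and 31-Dec-2009". The test is not tied to the index date.
- Section 3.1 starts the clock at a purchase: "Index date is defined as the date of first purchase of warfarin after 01-Jan-2007".
- Section 3.4.1 says that "follow-up for each time to event outcome continues until the time of the event, death, emigration or 31-Dec-2011 whichever comes first". The end of warfarin treatment or of INR testing is not a censoring event.

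Section 5 concedes that "All laboratory values for particular patients may then not be available", because the data come from separate local laboratories.

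**The concern.** The 60-day limit in method 2 implies that two tests further apart than this do not support interpolation. The plan nevertheless keeps those days classified, and uses less information to do so: the older test alone. The days on which INR is least well known enter the primary comparison with the same standing as days next to a test.

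The daily INR level is the exposure in all three primary objectives (thromboembolic events and myocardial infarction, bleeding, mortality). Days in the wrong level distort both the stratified incidence rates and the Cox hazard ratios against the 2.0-3.0 reference. The protocol aims to detect differences of 10-20%, so even modest distortion matters.

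New users raise a further issue. A test taken before the first purchase can satisfy the entry criterion and, if no other test follows, be carried into follow-up as if it reflected treatment.

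**Working it through.** **1. How long one test can label follow-up.** Inputs: eligible test dates 01-Jan-2007 to 31-Dec-2009 (section 3.2.1) and end of follow-up 31-Dec-2011 (section 3.4.1). Take a patient with no later test who is followed to the end.

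| Date of only test | Days to 31-Dec-2011 | Days beyond 60 | Share beyond 60 |
|---|---|---|---|
| 01-Jan-2007 | 1,825 | 1,765 | 96.7% |
| 31-Dec-2009 | 730 | 670 | 91.8% |

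These are extremes, not typical patients. The two methods contribute differently. The 60-day sentence in method 2 covers a gap between two tests, which closes at the next test. The open tail after the last test comes from method 1.

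**2. Whether another provision limits it.** The planned sensitivity analyses vary:

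- the exposure multiplier and the two-purchase requirement (section 4.1);
- history of AF (section 4.1.1);
- the gap that defines stopping warfarin (section 4.1.2);
- the surgical discontinuity period (section 4.1.3).

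None varies or caps the INR carry-forward. Comparing methods 1 and 2 does not test it either, because in gaps over 60 days both give the same carried value.

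**3. Possible dilution.** Assumptions, not document facts: a share q of person-time is stale; on stale days true INR is unrelated to the label and follows the shares in section 4.2 (21.7%, 63.6%, 14.7%); risk is raised only under 2.0, by a factor HR.

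- Mean relative rate on stale days: s = 0.217 × HR + 0.783
- Observed HR = [(1 − q) × HR + q × s] / [(1 − q) + q × s]

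For HR 2.0, s = 1.217:

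- q = 0.2: (1.6 + 0.2434) / (0.8 + 0.2434) = 1.77
- q = 0.4: (1.2 + 0.4868) / (0.6 + 0.4868) = 1.55

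For HR 1.5, s = 1.1085:

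- q = 0.2: (1.2 + 0.2217) / (0.8 + 0.2217) = 1.39
- q = 0.4: (0.9 + 0.4434) / (0.6 + 0.4434) = 1.29

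If half of the stale days still carry the right level, the effective q at 20% stale time is 0.1, and the results are 1.88 for HR 2.0 and 1.45 for HR 1.5.

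**4. Effect on power.** Table 4.2-1 gives 78.6% for relative risk 1.20, 1.5 events per 100 patient-years and 32,000 patients. Two-sided alpha 0.05 is assumed. With p = 21,000/82,000 and E = 82,000 × 0.015/0.985 = 1,249,

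power = Φ(√(E·p·(1 − p)) × ln 1.20 − 1.96) = Φ(15.42 × 0.1823 − 1.96) = 80.3%.

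This formula reproduces all 36 cells of the table within 2 points, so the table is not in dispute. It allots all 96,000 person-years to an INR level. Under the assumptions of step 3:

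| Stale share | Observed RR, carry-forward | Power, carry-forward | Power, stale days dropped (RR stays 1.20) |
|---|---|---|---|
| 10% | 1.18 | 72.0% | 76.0% |
| 20% | 1.16 | 62.2% | 71.1% |
| 30% | 1.14 | 51.5% | 65.3% |

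In this scenario, discarding stale person-time loses less power than keeping it.

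**The case against.** **The rule for stopping warfarin may bound the carry-forward.** Section 4.1.2 treats warfarin as ended after a gap of more than 2 months since the last exposure and INR measurement. Section 4.1 tests the exposure multiplier for the primary objectives, which suggests that purchase-based exposure enters the primary person-time. If so, the multi-year case needs a patient who keeps buying warfarin without a test in a participating laboratory. This stands as an ambiguity and makes the extreme rarer. It does not remove the problem: the stopping rule appears only under secondary objective 3, section 3.4.1 does not censor primary follow-up there, and on a literal reading continued purchases alone keep a patient on treatment.

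**A cap belongs in the SAP.** A separate SAP is promised and may add one. But the protocol is not silent here: it states the carry-forward rule and sets no limit on it.

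**Bias and frequency are not shown.** This stands. A reader might infer that long gaps are common and that hazard ratios must be pulled toward 1. Section 5 says only that values may be missing, and no distribution of test intervals is given. If test spacing depends on INR stability or on stopping warfarin, bias could go either way.

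**TTR is largely protected.** This also stands. A reader might infer that one in-range test makes a patient 100% in range for years. Section 4.1 computes interpolated TTR from tests in the previous 1, 2, 3, 6 and 10 months, so an older test drops out. The alternative TTR is a share of the previous 5 and 10 tests and uses no daily values.

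**A pre-treatment INR may be right at first.** In the first days after initiation, a level under 2.0 may be correct. The label misleads only when no later test replaces it.

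**Conclusion.** The point holds for the daily INR level. As written, the plan carries an INR forward without a maximum age, has no unknown level, and does not censor primary follow-up when treatment or testing ends. Following it misclassifies the exposure of the three primary objectives. Every day after a patient's first test is affected in principle; days before a first test have no value to carry.

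The missing limit and the 5-year extreme rest on the text and on date arithmetic. The size of the distortion does not: the fall from 2.0 to 1.77 or 1.55 depends on assumed stale shares of 20% and 40% and on stale labels unrelated to true INR, and partial agreement gives smaller falls. The documents establish neither the real stale share nor the direction of bias. Interpolated TTR is affected only within its 1-10 month windows, and measurement-based TTR not at all. The rule should be changed before analysis.

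**What to change.** Amend section 4.1 as follows.

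- In both daily INR methods, classify a day only if it lies within a stated maximum of the last INR, for example the protocol's own 60 days.
- For new users, do not carry an INR taken before the first purchase forward as an on-treatment value. For prevalent users, allow INRs from before the index date within the same limit: their index date is only the first purchase in the study window, and discarding earlier tests would lose valid on-treatment values.
- Put all other days in an 'INR unknown' level, kept as a separate category and out of the three-level contrast. Report its person-time and events.
- Run unlimited carry-forward and one alternative cap as sensitivity analyses.

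This takes a few sentences and no new data. The costs are fewer classified person-years and events, so somewhat wider intervals for a given effect, and possible selection if testing frequency is related to risk. Reporting the unknown level makes that selection visible.
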